Exploratory Endpoints	
Clinical Patient preferences and attitudes toward subcutaneous and intravenous

	
route of administration will be assessed based on questionnaires administered at enrollment and at study visits at month 6 and 12 post initiation of abatacept.
 
Immunologic/Mechanistic
 
 • CD86 receptor occupancy on PBMC will be assessed before the initial dose of abatacept, and prior to abatacept administration at months 9, and 12 months post-transplantation. • The incidence and breadth of anti-HLA antibody (including DSA) development over time (evaluated at screening, , 3, 6 and 12 post-transplant) • Peripheral blood T and B cell subsets will be assessed before initiation of abatacept and on study at 6, 9, and 12 months post - transplant.
Accrual Objective	18 patients will be enrolled into a single, investigational arm receiving abatacept
Study Duration	20 months, with the last new accrual no later than 12/31/2023.
Treatment Description	
Participants on qualifying belatacept regimen (with low dose tacrolimus, mmf and prednisone) will have their maintenance regimen changed from i.v. belatacept to s.c. abatacept, which will continue through week 52 (month 12) post-transplant:
 
Costimulation blockade:
 
 - Abatacept 125 mg subcutaneous weekly 
Background maintenance:
 
 - Tacrolimus initial trough target 3-5 ng/ml. - Mycophenylate mofetil (MMF), no less than 500 mg bid; comparable dose of mycophenolic acid (MPA) (no less than 360 mg bid) or azathioprine (AZA no less than 2mg/kg daily) may be used instead as maintenance dose. - Prednisone 5 mg po daily.
Inclusion Criteria	
 1. Must be able to understand and provide informed consent. 2. Male or Female, 18-70 years of age at the time of enrollment (all races and ethnicities). 3. Negative crossmatch (virtual or physical) at time of transplant 4. First dose of Study Drug must be given no less than 8 weeks, no more than 20 weeks post-transplant. 5. First time renal transplant who has been treated with belatacept from the time of transplant, receiving tacrolimus (target trough 3-5 ng/ml), mycophenylate mofetil (or mycophenolic acid or azathioprine), prednisone (also see exclusion criteria). 6. eGFR ≥ 40ml/min/m² (using 2021 CKD-EPI equation). 7. Must have prior documented evidence of EBV seropositivity.

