14.2.2 Primary Analysis of Primary Endpoint(s)

Primary feasibility endpoint

The proportion of subjects who tolerate subcutaneous injections and are compliant with self-administration as measured by abatacept administration logs, autoinjector accountability, pharmacokinetics and pharmacodynamic measures of target molecule (CD86) receptor occupancy.

Primary Effectiveness (alloimmunity) endpoint

This primary effectiveness endpoint is the proportion of participants who remain free of biopsy proven acute T-cell mediated rejection (aTCMR) or antibody-mediated rejection (ABMR) as defined by Banff criteria at or before 12 months after transplantation.

Primary Safety Endpoints

- The cumulative incidence of serious adverse events
- Incidence of serious infection of special interest (e.g. requiring hospitalization or prolonged therapy, including but not limited to treatment ≥ 20 days)
- Incidence of patients with CMV viremia stratified by magnitude (≥ 35 but $< 10,000$ or $\geq 10,000$)

- Incidence of patients with BK viremia stratified by magnitude (undetected, >0 but < 1,000, ≥ 1,000 but <10,000 or ≥ 10,000 – 100,000, ≥100,000 or stratified by log, which is reported as a result)
- Incidence of any malignancy including PTLN

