14.2.3 Analyses of Secondary and Other Endpoint(s)

Additional Effectiveness Endpoints

- Proportion of subjects experiencing the composite outcome of death or allograft failure at or before 12 months after transplantation.
- Proportion of subjects with biopsy proven acute T-cell mediated cellular rejection (BP-aTCMR) within 12 months of transplantation.
- Proportion of subjects treated for rejection with any of the following: i) corticosteroids within 12 months, ii) T-cell depleting therapy within 12 months, iii) any other treatment for rejection within 12 months of transplantation.
- Proportion of subjects treated for acute rejection due to clinical suspicion rather than BP-aTCMR or BP-aABMR) within 12 months of transplantation.
- Proportion of subjects with biopsy proven active antibody mediated rejection (BP-aABMR) within 12 months of transplantation.
- Proportion of subjects and time to event for the changes in allograft biopsies for the 5 categories of aTCMR specified in the Banff schema.
- Proportion of subjects who develop de-novo donor specific antibody by 12 months
- Change in eGFR between abatacept initiation and 12 months on treatment.
- Days to events (TCMR, ABMR, de-novo DSA formation, graft loss)

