14.4 Analysis Plan

Binary primary and secondary endpoints that occur at or before 12 months post-transplant will be summarized as a simple fraction and percentage and as a proportion. Confidence intervals (95%) for a one-sample proportion will be calculated for incidence rates using the Wilson score procedure with a correction for continuity.

Primary Effectiveness Endpoint: The cumulative incidence of alloimmunity (or alloimmunity-free survival) during the 12 months after transplantation will be estimated with the Kaplan-Meier method. The standard error of the Kaplan-Meier estimate will be calculated based on Greenwood's formula and used to construct 95% confidence intervals for the time-to-event curve. Patients with follow-up less than 1-year will be censored at last follow-up.

The cumulative incidence of primary safety endpoints during the 12 months after transplantation will be estimated with the Kaplan-Meier method.

A repeated-measures analysis of eGFR will be performed with a means model via the SAS MIXED Procedure (version 9.4; SAS Institute, Cary, NC), providing separate estimates of the mean eGFRs by time on study (between abatacept initiation and 12 months on treatment). The model will include one predictor (time on study as a categorical clinical visit variable). A compound-symmetric variance-covariance form in repeated measurements will be assumed for eGFR and robust estimates of the standard errors of parameters will be used to perform statistical tests and construct 95% confidence intervals (**Reference: Diggle et al**). The model-based means are unbiased with unbalanced and missing data, as long as the missing data are non-informative (missing at random). We will report the estimated mean eGFR and its 95% confidence at each month of follow-up and the time-averaged mean. A baseline-adjusted analysis will also be performed. Serum creatinine, total cholesterol, LDL, HDL, triglyceride and blood pressure plus the exploratory immunologic/mechanistic endpoints (peripheral blood T and B cell subsets) will be analyzed using the same plan described for eGFR.

This phase I trial will provide important estimates of variability (within-subject and between-subject standard deviation) for eGFR. The estimates of variability will be valuable to power future clinical trials since these variability estimates are essential components for sample size calculations.

15. Identification and Access to Source Data

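### Section 14.4 estimates cumulative incidence by Kaplan-Meier with deaths censored, which can slightly overstate rejection and most primary safety incidences, and it leaves alloimmunity-free survival undefined

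*Combined protocol and SAP*

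**What the plan says.** Section 14.4 (Analysis Plan) describes two ways of reporting the 12-month endpoints.

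- **Simple fraction.** Binary primary and secondary endpoints are summarized as a fraction and percentage. "Confidence intervals (95%) for a one-sample proportion will be calculated for incidence rates using the Wilson score procedure with a correction for continuity".
- **Curve.** For effectiveness, "The cumulative incidence of alloimmunity (or alloimmunity-free survival) during the 12 months after transplantation will be estimated with the Kaplan-Meier method", with Greenwood standard errors. For safety, "The cumulative incidence of primary safety endpoints during the 12 months after transplantation will be estimated with the Kaplan-Meier method".

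The only censoring rule is: "Patients with follow-up less than 1-year will be censored at last follow-up".

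Other sections bear on how these curves should be read:

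- Section 14.2.2 defines the effectiveness endpoint as freedom from biopsy-proven aTCMR or ABMR. Death and graft loss are not part of it.
- Section 14.2.3 has a separate secondary endpoint: "Proportion of subjects experiencing the composite outcome of death or allograft failure at or before 12 months after transplantation".
- Section 13.2.4 lists death as the first SAE outcome.
- Section 12.2.1 keeps patients in scheduled assessments after study therapy stops. No section ends follow-up at graft loss.

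No section mentions competing risks, defines alloimmunity-free survival, or says which of the two estimates is primary. Section 14.2 refers detail to a statistical analysis plan, but the combined document contains no further statistical text on this point.

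**The concern.** A patient who has died cannot later have a rejection, an infection or a malignancy. If the death is censored, Kaplan-Meier assumes that the patient's unseen future resembles that of the patients still at risk. 1-KM then estimates incidence as if death did not occur, whereas cumulative incidence is the share of treated patients who actually have the event. The first is never below the second, and it is strictly above whenever an event follows the death.

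The label in parentheses adds a second difficulty. It may mean only the complement of the incidence curve. It may also mean survival without rejection, with death as a failure. The two readings give different numbers for a coprimary endpoint. Sections 3 (Study Objectives synopsis) and 14.1 say the results are to inform Phase II or III design, so the rejection figure carried forward should have one meaning.

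**Working it through.** **Inputs.** The sample size is 18 (synopsis, Accrual Objective: "18 patients will be enrolled into a single, investigational arm receiving abatacept"). The estimator and censoring rule are those of section 14.4. The documents give no expected rejection or death rate for this trial, so the counts are assumed: 1 to 4 rejections and 0 to 2 deaths. The upper ends match the section 12.6 DSMB triggers of four rejections and two deaths. Deaths are in patients without a prior event, and follow-up is otherwise complete.

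**The plan's own figures.** The plan gives no number on this point. Its one reproducible design figure at this sample size is the section 13.9 table. For a true rate of 10%, P(at least one event) = 1 - 0.9^18 = 0.85, as stated. The other cells also reproduce.

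**Formulas, for R events and D deaths among 18.**

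- Aalen-Johansen: just before each event the all-cause survival estimate is r/18, where r is the number at risk. Each event therefore adds (r/18)(1/r) = 1/18, and the total is R/18, the simple fraction.
- 1-KM, all deaths before the first event (the worst ordering): R/(18 - D).
- 1-KM, all deaths after the last event: R/18.
- Largest excess: R/(18 - D) - R/18 = R·D / [18(18 - D)].
- Event or death as failure: (R + D)/18.

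**Results over all orderings.**

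| Events | Deaths | Fraction = Aalen-Johansen | 1-KM | Largest excess (points) |
|---|---|---|---|---|
| 1-4 | 0 | R/18 | R/18 | 0 |
| 1 | 1 | 5.6% | 5.6-5.9% | 0.33 |
| 2 | 1 | 11.1% | 11.1-11.8% | 0.65 |
| 3 | 1 | 16.7% | 16.7-17.6% | 0.98 |
| 4 | 1 | 22.2% | 22.2-23.5% | 1.31 |
| 1 | 2 | 5.6% | 5.6-6.3% | 0.69 |
| 2 | 2 | 11.1% | 11.1-12.5% | 1.39 |
| 3 | 2 | 16.7% | 16.7-18.8% | 2.08 |
| 4 | 2 | 22.2% | 22.2-25.0% | 2.78 |

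An intermediate ordering (rejection, death, rejection) gives 1 - (17/18)(15/16) = 11.5%. The same formula serves the safety curves. For a commoner event, 8 cases and one death give at most 8/306 = 2.6 points.

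**Naming gap.** For two rejections and one death, the complement of survival without rejection is (2 + 1)/18 = 16.7% if death counts as failure, against 11.1-11.8% if it does not.

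**Graft loss.** Take three rejections, two graft losses and no deaths. If the patients with graft loss stay in follow-up and in the risk set, 1-KM is 3/18 = 16.7%, the same as the fraction. It rises to 3/16 = 18.8% only if they are censored at graft loss before any rejection.

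**Scale.** For 2/18 the continuity-corrected Wilson 95% interval runs from about 2% to 36%. The Greenwood standard error with two rejections and up to two deaths is 7.4 to 8.3 points.

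**The case against.** The strongest reply is that little turns on this. The study is an exploratory single arm of 18 with no success threshold for this endpoint. The bias is at most a few points, inside an interval more than 30 points wide. The simple fraction, which does not censor deaths, is already planned. On size, that reply stands. It does not remove the point, because the plan does not say whether the fraction or the curve is primary, and the two disagree whenever a death precedes a later rejection.

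A reader might also infer stronger conclusions that the documents do not support.

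- **All safety incidence is overstated.** It is not. Death is an SAE under section 13.2.4, so it counts as an event for first SAE and does not compete with it.
- **Graft loss inflates the estimate too.** It does so only if patients are censored at graft loss, which no section states; section 12.2.1 continues follow-up after therapy stops. The Definitions also count re-listing, sustained low eGFR and continued dialysis as graft loss, and none of these removes the graft. The defensible statement is that the handling is unspecified.
- **The plan equates two different quantities.** The text does not show this. Given the section 14.2.2 definition, the parenthesis may well mean only the complement. If instead it counts death as failure, that survival curve has no bias from censored deaths. What the text supports is that the term is undefined.
- **Each death moves the composite by 1/18, or 5.6 points.** A death after rejection adds nothing, because that patient has already failed.

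**Conclusion.** The concern holds in a limited form. Kaplan-Meier with deaths censored is not an estimator of cumulative incidence for rejection, serious infection, CMV viremia, BK viremia or malignancy. The overstatement is conditional and small: zero with no deaths or only late ones, and at most about 1.3 points with one death or 2.8 with two, for up to four events among 18. The undefined label can shift the reported figure further, by 4.9 to 5.6 points in the example of two rejections and one death (16.7% less 11.8% or 11.1%).

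These sizes rest on assumed counts, on deaths in event-free patients, on otherwise complete follow-up, and on reading the last-follow-up rule as applying to deaths. The text implies that reading but does not spell it out. The gap is worth closing before analysis because the remedy costs nothing, not because it threatens the study's conclusions.

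**What to change.** In section 14.4:

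1. Estimate the cumulative incidence of rejection, serious infection, CMV viremia, BK viremia and malignancy with the Aalen-Johansen estimator, treating death as a competing event. First SAE needs no such change.
2. State whether graft loss competes with rejection or the patient stays at risk.
3. Delete the reference to alloimmunity-free survival, or define it as a separate composite and list the events that count as failure.
4. State whether the simple fraction with its Wilson interval or the curve estimate is primary.

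The cost is a change of wording; no new data are needed. If follow-up is complete apart from deaths, the Aalen-Johansen estimate equals the planned simple fraction, so the two reports will then agree.

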13.9 Study Ability to Detect Uncommon Safety Events

Adverse Events (AE) include serious infections (COVID-19, CMV disease, pneumonia, BK) and serious disorders (gastrointestinal, cardiac, vascular, PTLD). The table below addresses safety using adverse event probabilities based on the targeted enrollment of 18 patients. The table provides the binomial probabilities of observing 0, 1+, 2+ or 3 or more occurrences of an AE during follow-up.

Adverse Event Probabilities for n=18 treated patients

Event Rate (AE)	Probability [0 / 18 Events]	Probability [1+ / 18 Events]	Probability [2+ / 18 Events]	Probability [3+ / 18 Events]
0.05	0.40	0.60	0.23	0.06
0.10	0.15	0.85	0.55	0.27
0.15	0.05	0.95	0.78	0.52

Thus, we can be **85%** sure of observing at least one episode of a rare AE if the true rate of an AE is 10%.

Adverse Events and Laboratory Toxicities: All adverse events will be classified using the Common Terminology Criteria for Adverse Events (CTCAE). Each adverse event and each laboratory toxicity will be counted only once per participant as the most severe level reported during the first year of follow-up. Tabular summaries of the number of participants reporting each AE, for both treatment-related and unrelated AEs as well as just treatment related AEs, respectively will be reported. Adverse events and grade III or higher laboratory toxicities observed during the first year of follow-up will be reported by treatment group.

14. Statistical Considerations and Analytical Plan

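### Greenwood limits on the Kaplan-Meier curve for freedom from rejection (n = 18) break down at zero events and undercover at low rejection rates; the Wilson interval already planned should be named as the reported one.

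*Combined protocol and SAP*

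**What the plan says.** The synopsis sets the size: "18 patients will be enrolled into a single, investigational arm receiving abatacept". Sections 3.2 and 14.2.2 define the primary effectiveness endpoint as the proportion free of biopsy-proven acute T-cell mediated or antibody-mediated rejection by 12 months after transplantation.

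Section 14.4 reaches that endpoint twice.

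- As a proportion: "Binary primary and secondary endpoints that occur at or before 12 months post-transplant will be summarized as a simple fraction and percentage". The interval is also named: "Confidence intervals (95%) for a one-sample proportion will be calculated for incidence rates using the Wilson score procedure with a correction for continuity".
- As a curve: a paragraph labelled for the primary effectiveness endpoint plans a Kaplan-Meier estimate, with the standard error from Greenwood's "formula and used to construct 95% confidence intervals for the time-to-event curve". On incomplete follow-up it says: "Patients with follow-up less than 1-year will be censored at last follow-up".

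The section does not say on which scale (linear, log or log-log) the Greenwood limits are built, what is reported before the first event or when there is none, or which interval is primary. The next paragraph plans Kaplan-Meier estimates for the safety endpoints but names no interval for them.

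**The concern.** Greenwood's variance is a sum over event times, so it is zero until an event occurs. In 18 patients who must have had no earlier biopsy-proven rejection (Section 4.4, exclusion 5), a result of no rejections or very few is plausible. The paragraph written for the primary effectiveness endpoint would then yield limits with no width, and the usual normal approximation is poor with one to three events.

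No test of the rejection rate is planned, so an interval is the main inferential statement on effectiveness. The coprimary objectives include informing Phase II and III design. A band showing 100% to 100% from 18 patients would mislead that step.

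**Working it through.** **Inputs.** n = 18 (synopsis). Interval methods from Section 14.4. The documents state no rejection rate, so I assume 3% to 30%. This range includes the 5%, 10% and 15% that Section 13.9 uses for adverse events. One of nine patients (11%) in the earlier abatacept series had a rejection (Section 2.1).

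**Step 1: reproduce the plan's own table.** Section 13.9, "Adverse Event Probabilities for n=18 treated patients", gives the probabilities of 0, 1+, 2+ and 3+ events. The exact binomial reproduces all 12 cells; at a rate of 0.10, for example, 0.1501 / 0.8499 / 0.5497 / 0.2662 against the printed 0.15 / 0.85 / 0.55 / 0.27.

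**Step 2: zero events.** The chance is (1 − rate)^18: 0.95^18 = 39.7%, 0.90^18 = 15.0%, 0.85^18 = 5.4%, 0.80^18 = 1.8%. In each such trial the Greenwood standard error is 0 and the 12-month interval is 100% to 100%, or undefined, on every scale.

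The early part of the curve is affected whatever the rate. Time runs from transplantation, but Appendix 1 (footnote 1) allows enrolment only from week 8 and prior biopsy-proven rejection excludes. No qualifying event can fall before week 8, so the band has no width there in any dataset.

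**Step 3: intervals by event count.** Without censoring, x events give S = 1 − x/18 and Greenwood variance S(1 − S)/18.

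- Linear: S ± 1.96·√[S(1 − S)/18]. For x = 1: 0.9444 ± 1.96 × 0.0540 = 83.9% to 105.0%.
- Log-log: S^exp(±e), with e = 1.96·√[x/(18(18 − x))]/|ln S|. For x = 1, e = 1.960, giving 66.6% to 99.2%.

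| Events | Linear Greenwood | Log-log Greenwood | Wilson, continuity-corrected (planned) |
|---|---|---|---|
| 0 | 100 to 100 | undefined | 78.1 to 100 |
| 1 | 83.9 to 105.0 | 66.6 to 99.2 | 70.6 to 99.7 |
| 2 | 74.4 to 103.4 | 62.4 to 97.1 | 63.9 to 98.1 |
| 3 | 66.1 to 100.5 | 56.8 to 94.3 | 57.7 to 95.6 |
| 4 | 58.6 to 97.0 | 51.1 to 91.0 | 51.9 to 92.6 |

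Limits above 100% arise only on the linear scale with 1 to 3 events.

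**Step 4: coverage.** Add the binomial probabilities of the counts whose interval contains the true value, with a zero-event trial counted as a miss. At a 5% rate the linear interval contains 95% for x = 1 to 4 (coverage 60.1%), and the log-log interval for x = 1 and 2 only (94.2% − 39.7% = 54.5%).

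| Assumed rejection rate | Linear | Log-log |
|---|---|---|
| 3% | 42.0% | 40.6% |
| 5% | 60.1% | 54.5% |
| 10% | 84.3% | 82.2% |
| 15% | 93.5% | 90.4% |
| 20% | 88.5% | 93.1% |
| 25% | 94.1% | 93.7% |
| 30% | 91.9% | 97.7% |

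The planned Wilson interval covers 96.5% to 98.9% over 3% to 30%.

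**Step 5: censoring.** A simulation with an assumed 10% censoring (20,000 runs per rate) gives linear/log-log coverage of 58.5%/53.3% at 5%, 83.0%/80.4% at 10%, 92.9%/90.3% at 15% and 87.4%/93.4% at 20%. The picture does not change.

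**The case against.** The strongest reply is that the same section already plans a sound interval. The endpoint is defined as a proportion, the Wilson interval is assigned to binary primary endpoints, and at 18/18 it gives 78.1% to 100%. Greenwood is tied to the curve and is not said to replace it. This is a phase I exploratory study with no success threshold, and the study stopping rules in Section 12.6 use event counts. Section 14.2 also defers detail to a statistical analysis plan. Most of this stands and limits the point. It does not remove it: the paragraph written for this endpoint specifies Greenwood, nothing gives Wilson precedence, and no further analysis detail appears in the document as we have it.

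A reader might infer more than the text supports:

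- That the trial has no valid interval for rejection. It has one; what is missing is its status.
- That limits above 100% follow from the plan. They need the linear scale, which is not stated, together with 1 to 3 events.
- That coverage is poor throughout. It is poor at rates of about 10% or less. On the log-log scale the loss is mostly the zero-event case: among trials with at least one event, coverage is 96.3%, 90.4% and 96.7% at 3%, 5% and 10%.
- That few rejections are the plan's own expectation. No rate is given, and the Section 13.9 table concerns adverse events. One of nine in a rescue series and the exclusion of prior rejection make it plausible, no more.
- That the safety curves share the defect. Greenwood is named only for effectiveness; the safety Kaplan-Meier estimates have no named interval.
- That the two intervals contradict each other. A crude proportion and a censoring-adjusted curve are different summaries.
- That an exact binomial interval must replace Wilson. That is a preference.

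**Conclusion.** The point holds for the Kaplan-Meier limits of the primary effectiveness endpoint. As written, they have no width or are undefined before the first event, and at 12 months if nobody rejects (a 40% chance at an assumed 5% rate, 15% at 10%). Undercoverage is severe at assumed rates of 3% to 5%, moderate at 10%, and at 15% to 30% ranges from a few points below nominal to slightly above it. The exact coverage figures assume no censoring and count zero-event trials as misses; the rejection rate is an assumption throughout. The proportion's planned Wilson interval is adequate, so the remaining faults are the curve's limits and the missing statement of which interval is reported.

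**What to change.** In Section 14.4:

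1. Name the continuity-corrected Wilson interval, already planned, as the reported 95% interval for the 12-month rejection-free proportion, and state how patients with less than one year of follow-up enter its denominator.
2. For the Kaplan-Meier curve, replace plain Greenwood limits with a method valid at zero events. The beta product confidence procedure is one: with all 18 at risk and no events its lower limit is 0.025^(1/18) = 81.5%. At minimum, state log-log limits and use an exact or Wilson limit wherever no event has yet occurred.

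The cost is a few sentences, a short program and somewhat wider curve limits. No change to sample size, visits or data collection is needed.

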APPENDIX 1: SCHEDULE OF EVENTS

		Enrollment period is from Week 8 post transplant to week 20 post transplant ¹											
Visit (Months)	Screen	Post Transplant Mth 2	Post Transplant Mth 3	Post Transplant Mth 4	Post Transplant Mth 5	Post Transplant Mth 6	Post Transplant Mth 7	Post Transplant Mth 8	Post Transplant Mth 9	Post Transplant Mth 10	Post Transplant Mth 11	Post Transplant Mth 12	FC
Visit (Weeks)		8-11	12	16-19	20-23	24	28	32	36	40	44	52	
Visit Windows		+/- 5 days	+/- 5 days	+/- 5 days	+/- 5 days	+/- 5 days	+/- 5 days	+/- 5 days	+/- 5 days	+/- 5 days	+/- 5 day	+/- 5 day	
Informed Consent	X												
Inclusion/Exclusion Criteria	X												
Pregnancy Testing of WOCB (serum or urine)	X												
Questionnaires			X			X						X	
PRA-HLA Ab Screen	X					X						X	X
SAB I/II (DSA)	X		X (mo 3)			X						X	X
Hemoglobin A1c	X											X	
Hematology (CBC including differentials w/platelets)	X		X			X			X			X	X
Chemistry Panel	X		X			X			X			X	X
Viral Monitoring (BK and CMV)			X			X			X			X	X
Pharmacokinetics (PK) monitoring			X ²						X			X	X
Assessment of Adverse Events			→			→	→	→	→	→	→	→	X
Concomitant Medications Reviews			X			X	X	X	X	X	X	X	
Abatacept weekly administration			X			→	→	→	→	→	→	→	

		Enrollment period is from Week 8 post transplant to week 20 post transplant ¹											
Visit (Months)	Screen	Post Transplan t Mth 2	Post Transplan t Mth 3	Post Transplan t Mth 4	Post Transpla nt Mth 5	Post Transpla nt Mth 6	Post Transpla nt Mth 7	Post Transpla nt Mth 8	Post Transpla nt Mth 9	Post Transpla nt Mth 10	Post Transpl ant Mth 11	Post Transpl ant Mth 12	FC
Visit (Weeks)		8-11	12	16-19	20-23	24	28	32	36	40	44	52	
Visit Windows		+/- 5 days	+/- 5 days	+/- 5 days	+/- 5 days	+/- 5 days	+/- 5 days	+/- 5 days	+/- 5 days	+/- 5 days	+/- 5 day	+/- 5 day	
MMF ≥ 500mg p.o. BID	(X) ⁴	→				→	→	→	→	→	→	→	
Prednisone 5mg p.o. daily	(X) ⁴	→				→	→	→	→	→	→	→	
Tacrolimus (target trough 3-5ng/mL)	(X) ⁴	→				→	→	→	→	→	→	→	
Immunophenotyping		X				X			X			X	X
HLA DR/DQ Eplet Score		X											
Gene Expression		X				X			X			X	X

¹ Subjects will be enrolled no less than 8 weeks post transplant, no more than 20 weeks post-transplant. For subjects enrolled after Month 2, any study visit which occurred prior to subject enrollment does not apply.

² Initial PK test only required at first dose of Abatacept.

³ Collected when enrolled.

⁴ Doses required at enrollment.

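### The eGFR tests and 95% intervals use robust standard errors from 18 patients with no small-sample correction, so the intervals cover about 93% and the tests reject too often

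*Combined protocol and SAP*

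**What the plan says.** The protocol synopsis (Accrual Objective) states that "18 patients will be enrolled into a single, investigational arm receiving abatacept". Section 14.4 then says:

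- Model: "A repeated-measures analysis of eGFR will be performed with a means model via the SAS MIXED Procedure".
- Fixed effects: "The model will include one predictor (time on study as a categorical clinical visit variable)".
- Working covariance: "A compound-symmetric variance-covariance form in repeated measurements will be assumed for eGFR".
- Inference: "robust estimates of the standard errors of parameters will be used to perform statistical tests and construct 95% confidence intervals".
- Output: "We will report the estimated mean eGFR and its 95% confidence at each month of follow-up and the time-averaged mean".
- Scope: serum creatinine, lipids, blood pressure and the T and B cell subsets "will be analyzed using the same plan described for eGFR".

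No small-sample correction, denominator degrees of freedom, null hypothesis or test level is given for eGFR. Section 14.2 defers detail to a statistical analysis plan, and nothing in the text available adds a correction. The eGFR endpoint itself (Sections 3.3 and 14.2.3) is one change, from abatacept initiation to 12 months.

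In Appendix 1, the row "Chemistry Panel" is marked at screening and months 3, 6, 9 and 12. That gives 4 on-study eGFR time points, or 5 with screening.

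**The concern.** A sandwich covariance protects against a wrong working covariance when there are many independent patients. With 18, two things go wrong. The classical estimator divides by n, so it is biased downwards. It is also noisy, and the usual reference distributions take little or no account of that. Both errors make intervals too short and tests too liberal, even if compound symmetry is exactly true and no value is missing. The effect is small for one contrast and grows with the number of visits tested jointly, because a larger covariance matrix must be inverted from the same 18 residual vectors.

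At stake are the stated precision of the monthly eGFR means and of the change in eGFR, and the false-positive rate of any test for change in eGFR or in the outcomes analysed alongside it.

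**Working it through.** The documents give no error rate or coverage for eGFR, so there is no figure to reproduce.

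**Inputs.** n = 18 (synopsis). Visit is the only factor, the working covariance is compound symmetric and the standard errors are robust (Section 14.4). T = 4 or 5 eGFR time points (Appendix 1). T and B cell subsets: T = 3 (months 6, 9 and 12, Section 14.2.4) or T = 4 with study entry (Section 10.2). Assumptions: normal data, complete follow-up, a two-sided 5% level, and the classical sandwich with divisor n, because no correction is named. The plan names no degrees of freedom, so three references are shown: n − 1 = 17, within-subject (n − 1)(T − 1), and large-sample (z or chi-square).

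**Single mean or contrast.** With complete data the fitted means are the simple visit means. The sandwich variance is then the usual sample variance times (n − 1)/n, so the robust standard error is the usual one times √(17/18) = 0.972. True size is P(|t₁₇| > 0.972 × critical value). Relative width compares the interval with the exact one, whose critical value is 2.110.

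| Reference | Critical value | × 0.972 | Coverage | True size | Relative width |
|---|---|---|---|---|---|
| t, 17 df | 2.110 | 2.050 | 94.4% | 5.6% | 0.972 |
| t, 51 df (T = 4) | 2.008 | 1.951 | 93.2% | 6.8% | 0.925 |
| t, 68 df (T = 5) | 1.996 | 1.939 | 93.1% | 6.9% | 0.919 |
| z | 1.960 | 1.905 | 92.6% | 7.4% | 0.903 |

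The intervals are therefore about 3% to 10% too narrow.

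**Joint test of visit, if one is run.** Let p = T − 1. The robust Wald statistic W equals n/(n − 1) times Hotelling's T², so W/p = [n/(n − p)] × F(p, n − p). True size is P(F(p, n − p) > critical value × (n − p)/n).

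Example, T = 4 with within-subject df: the critical value F₀.₉₅(3, 51) is 2.786. Multiplying by 15/18 gives 2.322, and P(F(3, 15) > 2.322) = 11.7%.

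| T | n/(n − p) | 17 df | (n − 1)(T − 1) df | Chi-square |
|---|---|---|---|---|
| 3 | 1.125 | 6.8% | 8.4% | 10.0% |
| 4 | 1.200 | 8.6% | 11.7% | 13.4% |
| 5 | 1.286 | 10.9% | 15.8% | 17.6% |
| 11 | 2.250 | 46.1% | 61.1% | 62.7% |

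The scheduled eGFR visits (T = 4 or 5) give about 9% to 18%. The cell subsets (T = 3 or 4) give about 7% to 13%. The last row is for scale only and would need 11 complete monthly visits.

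**Simulation check** (within-subject df; 2,000 to 2,500 runs per setting; true correlation compound symmetric or autoregressive at 0.9). With complete data the joint size was 11.6% to 12.9% at T = 4 and 15.2% to 16.0% at T = 5. With 10% of values missing (autoregressive case) it was 11.6% and 15.2%. Coverage averaged over visits was about 92% to 94%.

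**After correction.** Scaling the variance by n/(n − 1) and using t on 17 df gives exactly 95% coverage with complete data. Referring W(n − p)/(np) to F(T − 1, n − T + 1) gives exactly 5%. In the T = 4 and T = 5 simulations this scaled test rejected 4.6% to 5.5% of the time.

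**The case against.** The strongest reply is that the plan commits to less than the larger figures suggest. Much of it stands.

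- **No joint test is written out.** Section 14.4 speaks only of statistical tests. Visit is the sole predictor, so a reader might infer a stated null of equal mean eGFR at every visit, but the documents state none. For the endpoint that is specified, the change to 12 months, the excess size is only 0.6 to 2.4 percentage points.
- **The 61% figure is not the plan's error rate.** A reader might take it from the promise of monthly estimates. It needs 18 patients with complete eGFR at 11 monthly visits. Chemistry is scheduled at 4 or 5 time points, first dose falls anywhere from week 8 to week 20, and footnote 1 of Appendix 1 drops visits before enrolment.
- **Degrees of freedom matter.** With 17 df, coverage is 94.4% and the loss is slight. The plan does not choose 17 df, and no choice examined restores the nominal level.
- **Inflation of many times nominal does not extend to every outcome.** The T and B cell subsets have 3 or 4 time points, so about 7% to 13% is the range. Lipids and blood pressure have no row in Appendix 1, so no rate can be derived for them.
- **The consequence is limited.** A reader might infer that the error favours the hypothesis of preserved renal function. It does not: rejecting no change too often works against that reading. The within- and between-subject standard deviations intended for future sample sizes do not depend on the robust standard errors.
- **The absence of a correction is read from silence.** That is true, and a separate analysis plan might supply one. The text available settles on robust standard errors and goes no further.

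What remains is that the method as stated is anti-conservative at n = 18 under every degrees-of-freedom choice examined.

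**Conclusion.** The inference for eGFR is wrong as written, by a modest amount. Nominal 95% intervals cover about 93% (92.6% to 94.4%) and are 3% to 10% too narrow, and a single-contrast test has true size of 5.6% to 7.4%. Any joint visit test at the scheduled chemistry time points would have true size of about 9% to 18% (11.7% to 15.8% with within-subject df), and much more if monthly visits were modelled.

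These figures assume complete normal data, 18 analysed patients and the classical sandwich. Fewer patients make it worse: with an assumed n of 14 and within-subject df, the joint sizes at 4 and 5 time points are 14.1% and 20.1%. Staggered entry also hurts: simulated coverage for the change to the latest time point fell to about 86%, although those runs modelled 8 and 11 visits.

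eGFR is a secondary endpoint and the cell subsets are exploratory. The primary endpoints do not use this model. The point is minor to moderate, and worth correcting because the remedy is cheap.

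**What to change.** In Section 14.4, or in the statistical analysis plan it defers to:

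1. Keep the compound-symmetric model, which directly supplies the within- and between-subject standard deviations the plan wants. An unstructured covariance would also address the error rate but would lose that split.
2. Specify a bias-corrected sandwich estimator with degrees of freedom based on the number of patients: for example, n/(n − 1) scaling with t on n − 1 df for single means and contrasts, and a Hotelling-type F on T − 1 and n − T + 1 df for any joint visit test.
3. State whether a joint test will be done and, if so, limit it to the scheduled visits.
4. Apply the same rule to creatinine, lipids, blood pressure and the cell subsets.

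Reverting to model-based standard errors is not a safe substitute. In the complete-data simulations at 4 and 5 visits they held 4.7% to 5.5% when compound symmetry was true, but gave 7.8% to 8.5% under autoregressive correlation.

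The cost is a few sentences and an analysis setting. Intervals become about 3% to 11% wider (1/0.972 = 1.03; 1/0.903 = 1.11). The correction is exact only with complete data: with staggered entry and 8 or 11 visits the scaled joint test still rejected 8.6% to 9.5% of the time in simulation, a further reason to keep any joint test to the few scheduled visits.
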